The Structured Clinical Interview for DSM-V-TR Axis-I Disorders (SCID) (First et al., 2015), and the Schedule for Nonadaptive and Adaptive Personality (SNAP) (Clark, 1993) will be administered during screening to assess past and present psychiatric illness and personality pathology. Each morning, starting at Study Visit 1, participants will complete the Daily Rating Form (Endicott et al., 2006) online, a 20-item questionnaire that assesses physical and mood symptoms that accompany ovarian hormone changes. Ratings are transmitted to the study team in real-time, which **will be used to monitor rapid mood changes throughout the study and ensuring participant safety.**

The following measures will be administered at according to table 1:

1. The Inventory of Depression and Anxiety Symptoms (IDAS-II) (Watson et al., 2007) is a 64-item self-report questionnaire that comprehensively assesses anxiety and depression symptoms, including ill temper (i.e., irritability), dysphoria, panic, social anxiety, appetite change, lassitude, well-being, suicidality, traumatic intrusions, and insomnia. The IDAS-II has excellent psychometric properties and has been validated in PND (Watson et al., 2007). The dysphoria, ill temper, wellbeing (inverse), panic, and suicidality scales will be used to determine hormone sensitivity status. Replicating our previous study, HS+ will be defined as a 30% increase in mood symptoms during hormone addback. The ill temper scale will be used as the measure of irritability to examine associations with behavioral and fMRI data (Hypotheses 1c and 2c).
2. The Behavioral Inhibition/Behavioral Activation (BIS/BAS) Scales (Carver & White, 1994) is comprised of four subscales—BIS, Reward Responsiveness, Drive, and Fun Seeking—and 20 items total that assess behavioral inhibition (anxiety) and behavioral activation (impulsivity). We will also include the 5-item Frustrative Nonreward Responsiveness Subscale (Wright et al., 2009) to quantify lowered approach motivation following FNR (Hypothesis 2a). The BIS/BAS scales are associated with neural markers of psychopathology (Beaver et al., 2006; Simon et al., 2010). Exploratory analyses will be conducted to assess associations between BIS/BAS, IDAS-II irritability, behavioral, and fMRI data.

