7.2 Statistical Methods

We have defined HS+ as a 30% or greater change in any of the IDAS-II mood scales, which include dysphoria, suicidality, ill temper (i.e., irritability), and wellbeing (i.e., reverse-keyed) during hormone addback or withdrawal, compared with the individual's own baseline using the equation below:

$$\% \text{ symptom change} = (\text{Addback score} - \text{Baseline score}) / \text{Baseline score}$$

Percent symptom change will be calculated for each of the IDAS-II scales listed above at both the addback visit (V6) and withdrawal visit (V7). If a participant has a percent symptoms change of 30% or greater on any of the IDAS-II scales listed, she will be classified as HS+. HS- is defined as less than 30% change in any of the IDAS-II mood scales.

We will only include those with confirmed HS+ and HS- in our planned analyses. Those with a history of PND confirmed to be HS- will be excluded from planned analyses. However, if we have enough subjects with a history of PND who are HS-, then they may be included as a separate group in exploratory analyses. Alternatively, if those with a history of PND who are HS- are not significantly different from those without a history of PND who are HS- in terms of our key outcome variables, then we will pool the groups to increase power.

The IDAS-II is scored using a 5-point Likert scale, ranging from 1 "Not at all" to 5 "Extremely." The scales we will use to determine hormone sensitivity and their ranges are listed in the table below:

IDAS-II Scale	Minimum Score	Maximum Score
Dysphoria	10	50
Suicidality	6	30
Ill Temper	5	25
Wellbeing	8	40

Missingness. We will use multiple imputation to correct for data determined to be missing at random, given that it is a reliable method for obtaining valid inferences in both behavioral and fMRI research (Rubin, 1987; Vaden et al., 2012). Data for dropouts will be compared with data for those who complete

the study to determine the extent to which excluding their data will introduce selection bias, and selection bias will be identified as a weakness in any resulting publications or presentations.

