Sensitivity Analysis. In addition to the statistical tests described below, we will use sensitivity analyses to evaluate the robustness of the study's main results to reasonable perturbations of the statistical methods and assumptions used and to help ensure reproducibility of the main results. Sensitivity analysis will address the inclusion/exclusion of questionable data values (i.e., outliers), the use of alternative methods of coping with missing values and dropouts, and modeling assumptions.

Hypothesis testing. We have detailed both the null and alternative hypotheses we will test below. For all hypothesis tests, we will use the Bonferroni method to correct for multiple comparisons. All hypothesis tests that are observed to be not statistically significant will be reported as being inconclusive. In accordance with the ICMJE and Consort Statement, all statistical estimates of population parameters will be tabulated along with confidence intervals. The interpretation of confidence intervals will be an integral part of the data analysis in concert with the statistical hypothesis tests.

Power calculations overview. We have based our power calculations on previous studies of similar effects (i.e, not pilot studies) with N greater than or equal to 30. Given that prior literature suggests large effect sizes for Aims 1 and 2, we believe that point-estimates will yield relatively accurate power calculations.

Aim 1: To determine the extent to which irritability is characterized by dysfunctional threat processing during reproductive hormone challenge relative to baseline in HS+ and HS-.

Null hypothesis 1: HS+ is not characterized by behavioral activation in the context of potential threat during periods of hormone change in the target population.

Alternative hypothesis 1: HS+ is characterized by behavioral activation in the context of potential threat during periods of hormone change in the target population. Given this hypothesis, we will test the following sub-hypotheses:

Null hypothesis 1a: HS+ is not characterized by threat attention bias during hormone addback relative to baseline in the target population.

Alternative hypothesis 1a: HS+ is characterized by threat attention during hormone addback relative to baseline in the target population.

Independent variables: Group (HS+ versus HS-) and Phase (Visit 3-baseline versus Visit 6-hormone addback)

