Dependent variable: Threat attention bias will be measured using the visual dot probe task at study visits 3 and 6. Threat attention bias will be calculated for the angry-neutral trials by subtracting the mean reaction time (measured in milliseconds) on trials where the asterisk

appears on the same side as the angry face from the mean reaction time on trials where the asterisk appears on the same side as the neutral face.

Analysis: 2x2 Repeated Measures ANOVA will be used to analyze the effects of Group (HS- vs. HS+) and Phase (baseline vs. hormone addback) on threat attention bias.

Power: We used G*Power 3.1 for Mac to calculate power. We anticipate an effect size $f=0.3$ based on a previous study of threat attention bias in those with and without mood dysregulation (Hommer et al., 2014). If we set $\alpha=.05$, we will have 87% power to reject the null hypothesis with a total sample size of $N=30$.

Null hypothesis 1b: HS+ is not characterized by reduced amygdala-medial PFC connectivity in response to threatening stimuli during hormone addback relative to baseline in the target population.

Alternative hypothesis 1b: HS+ is characterized by reduced amygdala-medial PFC connectivity in response to threatening stimuli during hormone addback relative to baseline in the target population.

Independent variables: Group (HS+ versus HS-) and Phase (Visit 3-baseline versus Visit 6-hormone addback)

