Power: We have not powered to the study to assess secondary hypotheses. We used G*Power 3.1 for Mac to calculate power. Prior research suggests the association between irritability and reactive aggression has a large effect size (Pearson’s $r=.6$) in a civilian population (Geniole et al., 2017). If we anticipate an effect size $r=.3$ and set $\alpha=.05$ (two-tailed), we will have 70% power to reject the null hypothesis with a HS+ sample size of $n=15$. There is not enough information to predict the strength of the association between irritability and subcortical activation in response to FNR.

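### Hormone-sensitivity status is assigned partly from mood at the visits where the primary task outcomes are measured, so shared visit-level mood can inflate the Group x Phase test

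*Combined protocol and SAP*

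**What the plan says.** For Hypotheses 1a, 1b and 2a, Section 7.2 crosses "Group (HS+ versus HS-) and Phase (Visit 3-baseline versus Visit 6-hormone addback". Hypothesis 2b uses the same two factors in a larger model. The outcome is taken at both visits; for Hypothesis 1a, "Threat attention bias will be measured using the visual dot probe task at study visits 3 and 6".

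The group label comes from the IDAS-II: "Percent symptom change will be calculated for each of the IDAS-II scales listed above at both the addback visit (V6) and withdrawal visit (V7"). A rise of 30% or more on any one of four scales makes a woman HS+, and "HS- is defined as less than 30% change in any of the IDAS-II mood scales". Clinical Assessments in Section 6 words it differently, for addback only: "Replicating our previous study, HS+ will be defined as a 30% increase in mood symptoms during hormone addback". The IDAS-II is given at Visits 1 and 3 before any drug, and neither is named as the baseline for the percentage.

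Table 1 places the IDAS-II, the scan and both behavioural tasks at Visits 3 and 6. Section 5.3 gives every woman the same drug sequence. Women with a history of PND who turn out HS- are left out of the planned analyses, although pooling is allowed if they do not differ from the HS- controls. The sensitivity analyses in Section 7.2 cover outliers, missing data and modelling assumptions. None addresses how the label is formed.

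**The concern.** Group is a post-treatment variable that shares a measurement occasion with the outcome. A woman who is low or irritable at Visit 6 for any reason is more likely to be labelled HS+. If mood moves task performance on the day, her task score shifts too. An unusually good day at Visit 3 acts the same way if Visit 3 is the IDAS-II baseline. The groups can then differ in task change with no hormone effect, and the 2x2 model cannot tell this from hormone sensitivity. There is no concurrent arm without hormones to show how often the 30% rule is met by chance.

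The plan itself supplies the mood-task link. Hypotheses 1c and 2c predict it at Visit 6, with 0.3 cited for threat bias. For aggression, "Prior research suggests the association between irritability and reactive aggression has a large effect size" (0.6). For these two endpoints the bias runs in the hypothesised direction. At stake is whether a significant interaction is reported as altered threat or reward processing in hormone-sensitive women when it may show only that mood and task moved together at one visit.

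**Working it through.** **1. The plan's own figure.** Hypothesis 1a states 87% power with f = 0.3, alpha 0.05 and N = 30. For a within-between interaction with m = 2 occasions, lambda = f² x N x m / (1 - rho). The repeated-measures correlation rho is not stated. At rho = 0.5, lambda = 0.09 x 30 x 2 / 0.5 = 10.8, and the noncentral F on 1 and 28 df gives 88.7%. Power is exactly 87% at rho = 0.47. The range is 61.2% at rho = 0 to 94.4% at rho = 0.6. The figure reproduces. The interaction test is a two-sample t test on change, and lambda = 10.8 corresponds to d = sqrt(10.8 x 4 / 30) = 1.2.

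**2. How small a mood change sets the label.** From the scale minima in Section 7.2:
- Ill Temper: 0.30 x 5 = 1.5, so 2 points.
- Suicidality: 0.30 x 6 = 1.8, so 2 points.
- Dysphoria: 0.30 x 10 = 3 points.

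Four scales at two visits give eight chances per woman.

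**3. Mechanism.** Let r be the within-visit correlation of mood with task score. With no hormone effect, the spurious standardised difference in task change is about r times the HS+/HS- gap (in SD) in mood change between the two outcome visits. It is zero when r = 0.

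**4. Size by simulation.** The null has no hormone effect, and mood is exchangeable over Visits 1, 3, 6 and 7. Four integer IDAS-II scales use the document's floors and ceilings. The 30% rule is applied, and 15 HS+ women with PND history are compared with 15 HS- controls on Visit 6 minus Visit 3 by two-sided t test, with up to 8,000 trials per cell. Assumed, because the documents give no values: scale means and SDs; a chance HS+ rate of 30, 50 or 73% in women with PND history; and 10% or the same rate in controls.

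Rejection at nominal 5%:

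| Basis of group | r = 0.3 | r = 0.5 |
|---|---|---|
| Visit 6 or 7 against Visit 3 (Section 7.2 rule, Visit 3 as baseline) | 6.5-15.7% | 8.7-37.0% |
| Visit 7 against Visit 3 | 6.0-8.8% | 7.4-16.2% |
| Visit 7 against Visit 1 | 4.6-5.2% | 4.6-5.6% |
| Enrolment history, no mood selection | 4.8-5.6% | 4.8-5.1% |

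At r = 0 the Section 7.2 rule rejects in 5.0-5.2%. Its spurious d is 0.13-0.36 at r = 0.3 and 0.22-0.62 at r = 0.5. The low ends come from a 73% chance HS+ rate in women with PND history and 10% in controls. With equal mood variability in both groups the rates are 14-16% and 32-37%. Under the addback-only wording in Section 6 (Visit 6 alone against Visit 3), r = 0.3 gives 9.0-21.3%.

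As a check, the noncentral t at 15 per group gives 15.7% for d = 0.36 and 37.4% for d = 0.62, in line with the top of each range.

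**5. After Bonferroni.** The plan does not state the number of tests. With four primary tests (assumed), the level is 0.05 / 4 = 1.25%. The Section 7.2 rule rejects in 1.4-5.7% per test at r = 0.3 and 2.5-18.4% at r = 0.5. The lowest figure is barely above nominal.

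**The case against.** The strongest reply is that mood and task moving together is what the study seeks: Aim 1 concerns irritability, and the design provokes irritability in order to find its substrate. That stands for a claim about irritability in general. It does not cover the central hypothesis in Section 2, which is about reproductive hormone change.

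Second, the groups are not made by bad-mood days alone. Status can come from Visit 7, and planned HS+ women have a PND history while planned HS- women are controls with no psychiatric history. Section 1.4 also reports that, under this challenge, depressive symptoms rose in women with PND history and not in controls. A reader might infer that the label is nothing but Visit 6 mood noise; the documents do not support that. These features dilute the bias, and they are why the lower ends of the ranges are modest. They do not remove it.

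Third, a reader might infer much larger error rates from Section 1.4. Converting t = 2.97 with 11 and 14 women gives 2.97 x sqrt(1/11 + 1/14) = 1.20 SD. Multiplying by 0.3 and 0.6 gives d = 0.36 and 0.72, hence rejection of 16% and 48%. That conversion is not secure. Section 1.4 does not call the test a comparison of change scores, and t = 2.97 on 23 df has two-sided p = 0.0069, not the stated p < .004. It concerns one scale under the previous study's label. It also treats the whole gap as non-hormonal and assumes the cited correlations hold for change. At 1.25% the same d values reject in 5.9% and 26%.

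**Conclusion.** The overlap is in the documents, and nothing in the plan tests its effect. For the two behavioural endpoints, the Group x Phase test rejects too often in the hypothesised direction if mood and task correlate within a visit: about 6.5-16% at r = 0.3 and 9-37% at r = 0.5 against 5%, and lower but still above nominal after Bonferroni. The rates rest on the assumed scale distributions and chance HS+ rates, and on Visit 3 as the baseline. The direction needs only a positive within-visit correlation. The 0.6 cited for aggression lies beyond the simulated range. For connectivity and subcortical activation the plan says there is too little information to predict the correlation, so no size can be given.

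This does not mean that any positive result would be an artefact. At r = 0.3 the spurious d of 0.13-0.36 is far below the planned effect (about 1.2 at rho = 0.5), so the bias adds false positives and would not usually explain an effect of planned size. The point is worth correcting in the SAP before analysis, with medium confidence in its size.

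**What to change.** Keep the primary analysis. Name the IDAS-II baseline visit, reconcile the two wordings of the HS+ rule, and prespecify two supportive analyses of each primary endpoint, with estimates and confidence intervals.

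(a) Group x Phase with HS status from data that use neither Visit 3 nor Visit 6 mood. One option is IDAS-II at Visit 7 against Visit 1. Another uses diary data already planned ("Each morning, starting at Study Visit 1, participants will complete the Daily Rating Form"): mood items averaged over addback days away from Visit 6, against pre-injection days away from Visit 3 in a comparable cycle phase, with the cut fixed in advance.

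(b) Group x Phase by enrolment history in all completers, about 15 + 6 = 21 women with PND history against 15 controls.

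Attribute a primary result to hormone sensitivity only if the estimate in (a) is of similar size to the primary one, with the meaning of similar stated beforehand, and report (b) alongside. Otherwise describe it as a mood-task association at Visit 6. Agreement in direction with (b) is not a useful test: (b) shares most women with the primary analysis, and in no-hormone simulations it agreed with 93-100% of false positives.

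The cost is SAP wording and two extra models per endpoint on data already planned. Both analyses are less precise than the primary one. The Visit 7 label misses women who respond only at Visit 6, the diary label needs a new cut, and stress lasting several days could still link diary mood to Visit 6. Analysis (b) is diluted by women with PND history who do not respond.

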The objective of the current project is to extend this line of work by examining whether hormone sensitive women (HS+; n=15) show differences in the behavioral activation system relative to non-hormone sensitive women (HS-; n=15) under baseline and hormone challenge conditions using functional magnetic resonance imaging (fMRI) and behavioral tests. Our central hypothesis is that reproductive hormone changes are associated with dysregulated threat and reward processing and consequent irritability in HS+. The rationale for the proposed study is that employing a scaled down model of puerperal hormonal events permits the identification of a group of individuals homogeneous for hormone sensitivity (HS+), hence creating the best opportunity for disentangling the specific changes in brain function due to reproductive hormones (i.e., HS-) from those accompanying reproductive hormone-precipitated affective dysfunction (i.e., HS+). Because women will act as their own controls across time, this study design also allows for a powerful evaluation of state and trait variables that may contribute to irritability, including both threat processing and reward processing. Identifying both state and trait markers of irritability, and disentangling them from the effects of reproductive hormones on brain and behavior, will allow for the identification of neural substrates of irritability susceptibility that can be investigated across neuropsychiatric disorders. We plan to accomplish the objectives of this application by pursuing the following specific aims:

Aim 1: To determine the extent to which irritability is characterized by dysfunctional threat processing during reproductive hormone challenge relative to baseline in HS+ and HS-.

Hypothesis 1: We hypothesize that HS+ is characterized by behavioral activation in the context of potential threat. Given this hypothesis, we expect that:

Hypothesis 1a: Compared with HS-, HS+ will show a greater degree of threat attention bias as measured by the visual dot probe task during hormone addback relative to baseline.

Hypothesis 1b: Compared with HS-, HS+ will show reduced amygdala-medial PFC connectivity in response to threatening stimuli during hormone addback relative to baseline.

Hypothesis 1c (secondary): HS+ will show a significant association between self-reported irritability and 1) threat attention bias, and 2) amygdala-ventrolateral PFC connectivity during hormone addback.

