3.2 Outcome Variables

The primary endpoints for this aim are 1) threat attention bias assessed during the visual dot-probe paradigm, 2) amygdala-medial PFC connectivity in response to threatening faces on the implicit emotion face processing task in HS+ (compared with HS-) during hormone challenge relative to baseline. The secondary endpoints for this aim are the 1) correlation between IDAS-II irritability and threat attention bias, and 2) correlation between IDAS-II irritability and amygdala-medial PFC connectivity in HS+.

4 Subject Selection and Withdrawal

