Scanning is performed using a Siemens Prisma scanner at the UNC BRIC, which includes built in pulse oximetry capability. During each scanning session, participants will wear a pulse oximeter on their finger to record heart rate for the duration of time in the scanner. Evidence supports that monitoring autonomic nervous system activity during fMRI can provide insight into stress adaptability (Butle & Wartolowska, 2017). Whole-brain functional images will be acquired using a single-shot, gradient recalled echoplanar pulse sequence sensitive to blood-oxygen-level-dependent (BOLD) contrast. Each of 2 runs will consist of the acquisition of 195 successive brain volumes. FMRI image preprocessing, processing, and analysis will be conducted using FSL and custom MATLAB scripts.

FMRI analyses will include a block-design analysis for the implicit face emotion processing task and event-related BOLD response analysis for the Affective Posner Task within a priori selected regions of interest, including corticolimbic regions (amygdala, medial PFC) for the implicit face task and amygdala and striatum (caudate, putamen, nucleus accumbens) for the Affective Posner. Image analyses will control for any group differences in reaction time or accuracy.

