Dependent variable: Amygdala-medial PFC connectivity will be assessed during the implicit face emotion processing fMRI task at study visits 3 and 6. Functional connectivity expresses the statistical dependency among activations in different brain regions and results in undirected (symmetrical) connectivity matrices and will be calculated according to standard procedures (Walsh et al., 2017). We will use a generalized psychophysiological interaction (gPPI) approach for detecting context-dependent functional connectivity (Cisler et al., 2014; McLaren et al., 2012). Replicating the methods of Walsh et al. (2017), we will use an ROI approach to target the amygdala, which will be defined using the Harvard-Oxford subcortical atlas. Voxel-wise models will be used to evaluate connectivity with the amygdala seed. For each participant, mean fMRI time courses will be extracted from the amygdala seed using the “fslmeans” program in FSL, then multiplied by each psychological regressor of interest (i.e., task condition) to form the PPI interaction terms. The gPPI model will include physiological and psychological regressors, as well as their interaction terms to describe the unique effect of these interactions above and beyond the main effects of seed time courses and task conditions. Our primary contrast of interest will evaluate the difference between connectivity during presentation of threatening stimuli versus non-threatening stimuli. This allows for the characterization of connectivity patterns specific to threat processing.

Analysis: Group and phase differences will be evaluated with respect to seed-based connectivity specific to threat processing using a 2x2 mixed effects analysis with Bayesian estimation techniques with FMRIB Local Analysis of Mixed Effects (Smith et al., 2004).

Clusters will be thresholded at $Z>2.58$ or $p<.005$ corrected with a minimum contiguous cluster size of 8 (Walsh et al., 2017).

Power: We used G*Power 3.1 for Mac to calculate power. While few studies have examined changes in amygdala-PFC between those with and without depression following treatment, the few extant studies yielded large effects ($d=1.3$) (Straub et al., 2017). If we anticipate an effect size $f=.5$ and set $\alpha=.05$, we will have greater than 99% power to reject the null hypothesis with a total sample size of $N=30$.

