Null hypothesis 1c (secondary): In HS+, the degree of irritability, threat attention bias, and amygdala-medial PFC connectivity during hormone addback are unrelated in the target population.

Alternative hypothesis 1c (secondary): In HS+, irritability is associated with 1) threat attention bias, and 2) amygdala-medial PFC connectivity during hormone addback in the target population.

“Independent” variable: Irritability will be defined as scores on the IDAS-II ill temper scale at study visit 6.

“Dependent” variables: Threat attention bias at study visit 6 will be calculated in the same way as for hypothesis 1a. Amygdala-medial PFC connectivity at study visit 6 will be calculated in the same way as for hypothesis 1b.

Analysis: Pearson’s r will be calculated for correlations between irritability and 1) threat attention bias and 2) amygdala medial-PFC connectivity during hormone addback (study visit 6) in HS+.

Power: We have not powered to the study to assess secondary hypotheses. We used G*Power 3.1 for Mac to calculate power. Prior research suggests the association between irritability and threat attention bias has a medium effect size (Spearman’s $\rho=.3$) (Hommer et al., 2014). If we anticipate an effect size $\rho=.3$ and set $\alpha=.05$ (two-tailed), we will have less than 20% power to reject the null hypothesis with a HS+ sample size of $n=15$. There is not enough information to predict the strength of the association between irritability and amygdala medial-PFC connectivity.

Aim 2: To determine the extent to which irritability is characterized by dysfunctional reward processing during reproductive hormone challenge relative to baseline in HS+ and HS-.

Null hypothesis 2: HS+ is not characterized by increased frustration in the context of non-reward (i.e., when reward is expected) during hormone addback relative to baseline in the target population.

Alternative hypothesis 2: HS+ is characterized by increased frustration in the context of non-reward during hormone addback relative to baseline in the target population. Given this hypothesis, we will test the following sub-hypotheses:

Null hypothesis 2a: HS+ is not characterized by reactive aggression during hormone addback relative to baseline in the target population.

Alternative hypothesis 2a: HS+ is characterized by reactive aggression during hormone addback relative to baseline in the target population.

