Independent variables: Group (HS+ versus HS-) and Phase (Visit 3-baseline versus Visit 6-hormone addback)

Dependent variable: Reactive aggression will be defined as the number of point subtractions the participant makes during the Point Subtraction Aggression Paradigm.

Analysis: 2x2 Repeated Measures ANOVA will be used to analyze the effects of Group (HS- vs. HS+) and Phase (baseline vs. hormone addback) on threat attention bias.

Power: We used G*Power 3.1 for Mac to calculate power. We anticipate a large effect size based on a previous study examining reactive aggression using the Point Subtraction Aggression Paradigm in men who were treated with testosterone versus placebo ($d=.95$) . If we estimate the effect size $f=.45$ and set $\alpha=.05$, we will have greater than 99% power to reject the null hypothesis with a total sample size of N=30.

Null hypothesis 2b: HS+ is not characterized by reduced activation of the amygdala and ventral striatum in response to FNR during hormone addback relative to baseline in the target population.

Alternative hypothesis 2b: HS+ is characterized by reduced activation of the amygdala and ventral striatum in response to FNR during hormone addback relative to baseline in the target population.

Independent variables: Group (HS+ versus HS-) and Phase (Visit 3-baseline versus Visit 6-hormone addback)

Dependent variable: Activation in amygdala and ventral striatum (caudate, putamen, nucleus accumbens) ROIs during the Affective Posner Task. Event types include three categories: trial type (money, no money), validity (valid, invalid), and feedback (positive, negative, error). Combination of these three factors will be modeled using individual linear regression with a fixed-shape, gamma-variate response function, convolved with a boxcar function of the stimulus duration. FNR will be defined as the contrast between positive valid money trials and negative valid money trials (i.e., the difference between expecting money and getting it and expecting money and not getting it).

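### Section 7.2 needs one outcome corrected (2a) and two analysis decisions fixed before data are seen: which test answers 2b, and what threshold and medial PFC measure define 1b

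*Combined protocol and SAP*

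**What the plan says.** **2a (Section 7.2).** The dependent variable is clear: "Reactive aggression will be defined as the number of point subtractions the participant makes". The Analysis line then applies a 2x2 repeated-measures ANOVA to the effects of "Group (HS- vs. HS+) and Phase (baseline vs. hormone addback) on threat attention bias".

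**2b (Section 7.2).** The Dependent variable paragraph lists trial type (money or no money), validity, and feedback (positive, negative or error). It defines FNR as positive against negative feedback within valid money trials. The Analysis paragraph keeps two event-type regressors to model FNR, extracts mean signal per ROI and event type, and enters the values in an ANCOVA with factors Group, Trial type, Feedback, Phase and Region. Section 6 describes the Affective Posner Task in three runs: a practice run without winnings outside the scanner, then two runs played for money. The Study Summary and Appendix C (Statistical analysis strategy) describe a 2-by-2 design, and Appendix C makes the group-by-time interaction the principal effect.

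**1b (Section 7.2).** The amygdala seed has an atlas. On the target side, "Voxel-wise models will be used to evaluate connectivity with the amygdala seed", and the decision rule is "Clusters will be thresholded at $Z>2.58$ or $p<.005$ corrected with a minimum contiguous cluster size of 8", credited to a cited study. Section 6 places the fMRI analyses "within a priori selected regions of interest, including corticolimbic regions (amygdala, medial PFC) for the implicit face task". For 1c, Section 7.2 says "Amygdala-medial PFC connectivity at study visit 6 will be calculated in the same way as for hypothesis 1b".

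**The 1c target region.** Section 2 has "amygdala-ventrolateral PFC connectivity during hormone addback". Section 3.2 has "correlation between IDAS-II irritability and amygdala-medial PFC connectivity in HS" (HS+ women), and Section 7.2 and the Appendix C overview also say medial.

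**The concern.** Appendix C lists these three outcomes among the four primary endpoints, and each lacks something the analyst needs.

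- **2a:** followed literally, the line repeats the 1a analysis and leaves reactive aggression untested.
- **2b:** the analyst must choose a term from a five-factor model after the data exist, and two plausible choices answer different questions.
- **1b:** a reader cannot tell whether a reported cluster is controlled for multiple testing. The 1c correlation needs one connectivity number per woman, and no rule produces it.

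Section 7.2 also promises Bonferroni correction for all tests. The number of tests cannot be counted until the 2b regions and the 1b measure are settled.

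**Working it through.** **The plan's own power figures.** For a within-between interaction, lambda = f² x N x m / (1 - rho), with N = 30, m = 2 visits and df 1 and 28. The plan gives no correlation between visits; rho = .5 is assumed here.

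- 1b and 2b, f = .5: lambda = .25 x 30 x 2 / .5 = 30, power 99.96% (stated: greater than 99%).
- 2a, f = .45: lambda = .2025 x 60 / .5 = 24.3, power 99.7% (stated: greater than 99%).
- Section 7.1, d = 1.10, 15 per group, two-sided t test: 82.8% (stated: 80%).

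The Section 7.2 figures fit a Group x Phase test on one value per woman per visit. That is the design in the Study Summary and Appendix C.

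**2a.** The hypothesis, the dependent variable and the power text all concern reactive aggression. Only the Analysis line names another outcome.

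**2b, Trial type.** The list of event types allows two levels of Trial type. The FNR definition, the two regressors and the Section 6 run description allow only one, money. The texts cannot all describe the same model.

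**2b, which term.** Let P and N be a woman's change from visit 3 to visit 6 in the response to positive and to negative feedback in valid money trials. Assume each has SD 1 and their correlation is r.

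- Group x Phase on event-level values compares the groups on (P + N)/2, with SD = sqrt((1 + r)/2). At r = .5 this is .866.
- The FNR contrast compares them on N - P, with SD = sqrt(2(1 - r)). At r = .5 this is 1.00.

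The effect size of 1.10 is borrowed from Section 7.1. With 15 per group and alpha .05 two-sided, the noncentral t (df 28) gives:

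| Assumed group difference | Group x Phase: d, rejects | FNR contrast: d, rejects |
|---|---|---|
| 1.10 in both P and N (no FNR effect) | 1.10/.866 = 1.27, 92% | 0, 5% |
| 1.10 in N only | .55/.866 = .64, 39% | 1.10/1.00 = 1.10, 83% |
| .55 in opposite directions | 0, 5% | 1.10/1.00 = 1.10, 83% |

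For r = .3 and r = .7 respectively, Group x Phase in the first row becomes 95% and 88%, and in the second row 44% and 35%. The FNR contrast in the last two rows becomes 69% and 96%. A simulation of 20,000 trials per setting agrees within about one percentage point.

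**2b, an equivalence and its limit.** Group x Phase on the FNR contrast is the same test as Group x Feedback x Phase only if the model holds valid money trials and two feedback levels. With the third level, error, the latter has two numerator degrees of freedom. With no-money trials in the model, it averages over money and no-money.

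**1b threshold.** Z = 2.58 corresponds to p = .0049 one-sided or .0099 two-sided, both uncorrected. Conversely, p = .005 is Z = 2.576 one-sided or 2.807 two-sided. The two halves of the rule therefore agree only if .005 is a one-sided, uncorrected voxel threshold. The sentence says corrected, and it names no method, search volume or unit for the cluster size.

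**1b measure.** Section 7.2 builds a gPPI model for each participant and names the threat-versus-non-threat contrast. It does not give a medial PFC mask or a rule for averaging the contrast over that region.

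**The case against.** The strongest reply is that the intent can be recovered. The 2a line is evidently a copying slip, since everything around it concerns point subtractions. A full five-factor ANCOVA contains Group x Feedback x Phase, so an FNR test is available inside the printed model. Medial PFC is an a priori region, the per-participant contrast is defined, and the threshold is credited to a study that may specify the correction. 1c is secondary and openly unpowered.

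Much of this stands, and it rules out several stronger readings:

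- A reader might infer that the plan tests 2b with Group x Phase and so tests the wrong thing. It does not say so: Group and Phase are listed as independent variables, but no term is selected. The defect is the missing choice.
- A reader might take 5% against 83% as the size of the 2b problem. That row is the extreme case by construction; the 39% against 83% row shows a smaller gap.
- A reader might infer that 1b has an inflated false-positive rate. Any such rate requires ignoring the word corrected and assuming a mask size and smoothness that the plan does not give.
- A reader might infer a contradiction between four ROIs in Section 7.2 and two in Appendix C. The Section 7.2 wording puts three nuclei in brackets after striatum, so it can be read as two. The count needs stating, but no conflict is proved.

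Recoverable intent does not settle the 2b term, the 1b correction or the value that enters 1c. Those are choices, and as the plan stands they would be made after the data are available.

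**Conclusion.** The point holds at the level of should-fix.

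- **2a** is wrong as written, though its meaning is not in doubt.
- **2b** is wrong as written: the texts disagree on Trial type, no test term is named, and the model's Group x Phase term is not an FNR test. The choice of term can reverse the conclusion: 92% against 5% with a common shift, 39% against 83% with a negative-feedback shift only. These figures assume a 1.10 SD change-score effect and correlation .5, and neither is a plan value for this contrast.
- **1b** is a cheap improvement: the threshold contradicts itself arithmetically and the target lacks a mask and an averaging rule. No error rate can be attached to it from the documents.

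Nothing here shows that the stated power or the sample size is wrong.

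**What to change.** **2a.** Replace the outcome in the Analysis line with the number of point subtractions.

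**2b.** Reconcile Section 6 and the two 2b paragraphs on whether no-money trials are scanned and modelled. Make the primary test Group x Phase on each woman's FNR contrast (negative versus positive feedback, valid money trials), and state the direction of subtraction so that reduced activation has one meaning. State whether the regions count as two or four, and whether they are averaged or alpha is split.

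**1b and 1c.** Define one medial PFC mask. Test Group x Phase on the mean threat-minus-non-threat gPPI estimate in it at the Bonferroni alpha, and use the visit 6 value in 1c. Report voxel-wise maps as exploratory, or with a stated cluster-level family-wise correction. An ROI mean is one reasonable choice; its downside is that localisation is no longer primary. Align the region in Section 2, Hypothesis 1c, with Sections 3.2 and 7.2 and Appendix C.

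**Cost.** Text, one mask and one named test per hypothesis, with no added participants or visits. Bonferroni already applies: if the family is the four primaries, power at d = 1.10 falls from 83% at .05 to 64% at .05/4 = .0125. Splitting the 2b share would lower it to 53% for two regions (.00625) or 43% for four (.003125). Averaging over regions avoids that alpha split.
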